4.1.1 General Design Description

A clustered, multiple-baseline design will be used to examine the impact of the implementation support condition on clinicians' fidelity, use and ratings of MBC appropriateness, acceptability and fidelity. Approximately 50 SMH clinicians will be recruited to participate from two school districts. All clinicians will receive the same implementation supports; there is no random assignment to condition. Following an initial control period of at least 1 month, school districts will start receiving implementation supports. During the initial control period, baseline MBC use, attitudes, acceptability, feasibility and appropriateness (per clinician self-report) will be collected, as well as needs assessment data from clinician surveys to inform necessary adjustments to the implementation supports. Baseline engagement and student outcomes will be collected after initial clinician training session. MBC implementation outcomes (i.e., MBC use, attitudes, acceptability, appropriateness, and feasibility), engagement and student outcomes will be collected at 3-month and 6-month follow-up during intervention supports, plus a 9-month follow-up interval. This allows clinicians in the two school districts to be compared to each other and to their own baseline. The primary comparison is pre-post ratings of implementation outcomes for all N=50 clinicians. The secondary comparisons are pre-post ratings of engagement and student outcomes, and between-agency differences.

Study Date Range and Duration

This study is expected to last approximately one calendar year from recruitment to follow-up, aligned with the 2021-2022 and 2022-23 academic years as the participating sites are school districts. Clinicians will start training and consultation in the fall of 2021 or 2022 and parents/guardians will be recruited in the fall of 2021 or 2022. Data collection will occur at baseline, 3 months, 6 months and 9 months.

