4.3.1 Number of Participants

We plan to work with 50 SMH clinicians and up to 150 parents of children or adolescents with mental illness receiving MBC in SMH services. All SMH clinicians at each district will be invited to participate, and we anticipate approximately 10-40 clinicians from each district depending on their size. All 150 parents of children and adolescents with mental illness receiving MBC in SMH services will be invited to participate. The rationale for this sample size is based on having a large enough sample of clinicians trained that a range of implementation outcomes can be observed and described as pilot data for a larger-scale, fully-powered study. The rationale for the 150 students is based on our prior research in quality improvement and implementation research in schools, where it is more feasible to introduce a new practice to clinicians by telling them they can select a subset of their caseload for MBC implementation. We will outreach to students the clinician reports they are using MBC with. Selection of a subset of cases will involve a random selection of recently consented cases.

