4.3.2 Eligibility Criteria/Vulnerable Populations

Parent/Guardian Participants

To be eligible for inclusion in the study, a parent or legal guardian must meet all of the following criteria:

- Female, male or other gender ≥ 18 years of age at the time of recruitment.
- Parent or legal guardian of a child age 5 to 18 at the time of recruitment who is enrolled in school-based mental health treatment services with one of the clinician participants included in the study (see inclusion criteria for clinician participants above).
- Enrolled in school-based mental health services within 3 months prior to the recruitment date.
- English speaking.
- Ability to provide informed consent.

Parents/guardians who do not meet all inclusion criteria are excluded. There are no other exclusion criteria.

5 Study Methods/Procedures

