ORS/SRS Acceptability	Usage Rating Profile – Assessment (URP-A)			3M follow up 6M follow up 9M follow up
Fidelity (MBC Use)	Retrospective coding of PCOMS measures (SRS, ORS)	Chart review and/or BON system	Study Team	Monthly
Student Engagement	Session Rating Scale (SRS)			
Student Functioning	Outcome Rating Scale (ORS)			
Student Symptoms	Pediatric Symptom Checklist (PSC-35)	Phone	Parent	Baseline* 3M follow up 6M follow up 9M follow up
Parent Engagement	Therapeutic Alliance Scales for Caregivers and Parents			

**after clinician consent, near initial clinician training*

Secure Data Recording and Maintenance:

Online survey data will be maintained in the PI's Yale Qualtrics account, accessible only by members of the study team listed on the IRB protocol. Online survey data will be downloaded and maintained on secure Yale storage servers and networks (i.e., Yale Box, network drive). Clinicians will provide their identifying information (name, email address) when they consent as well as a secure 4-digit anonymous code. They will be asked to submit this same 4-digit code with each follow-up survey. This will ensure the study team can track individual clinician responses over time, but each survey is completed confidentially. A password-protected Excel file including clinician identifying information and 4-digit codes will be maintained on secure Yale storage servers and networks, accessible only to study team members.

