Chart review data may be in various formats depending on the format of documentation and storage systems at each district (study site). We only need basic information such as child diagnosis, date entered services, treatment goals, and number of sessions attended. We will also ask for their anonymous BON code so we can link those data (see below). Consistent with best practices in chart review methodology, we will work with each district to identify a "data extractor" at their site who can obtain the relevant data for students of consented parents within the requisite time frame and prepare them for the study team. Our team will provide a list of names of children based on parental consent obtained, as well as the data we are requesting. Once we receive the chart data, we will deidentify it with a unique study identifier and keep the list of linked study IDs to names in a separate password-protected file. We expect that the requested chart review material can be transferred in electronic format to our site at Yale, we will use Yale's secure file transfer system, save the material on our secure Yale storage server or network, and then complete the enter the services data for each child. These files will be saved on our secure Yale storage server and network and entered into a database.

BON/PCOMS system data (including the Outcome Rating Scale and Session Rating Scale) will be maintained in the Better Outcomes Now (www.betteroutcomesnow.com) secure online system. Clinicians enter these data directly into PCOMS using their own anonymous code for students. There are no identifiable information in PCOMS. Our study team will be the PCOMS trainers and also have administrative privileges in PCOMS to support MBC

implementation. In order to protect the confidentiality of parents consenting to the study, the study team will not share the names of consented families with clinicians in order to access their PCOMS data. Instead, we will use aggregate, deidentified PCOMS data at the clinician level to estimate MBC fidelity. This is a HIPAA-compliant site developed specifically for secure progress monitoring data entry and viewing my clinicians and their clients.

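### The secondary pre-post student comparison starts from a post-training baseline taken up to 3 months into services, and the student models do not name time in services

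*Combined protocol and SAP*

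**What the plan says.** The two kinds of baseline are timed differently. For clinicians, section 4.1.1 says: "During the initial control period, baseline MBC use, attitudes, acceptability, feasibility and appropriateness (per clinician self-report) will be collected". For students and parents, the synopsis and section 4.1.1 both say: "Baseline engagement and student outcomes will be collected after initial clinician training session". The footnote to Table 1 in section 5.1.1 is looser and places the parent baseline "after clinician consent, near initial clinician training". Section 4.1.1 then states: "The secondary comparisons are pre-post ratings of engagement and student outcomes, and between-agency differences".

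On who is measured, one inclusion criterion in section 4.3.2 reads "Enrolled in school-based mental health services within 3 months prior to the recruitment date". Section 4.3.1, repeated in 5.3.2, says "We will outreach to students the clinician reports they are using MBC with".

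On what is recorded, section 5.1.1 requests "child diagnosis, date entered services, treatment goals, and number of sessions attended" for children of consented parents.

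On the analysis, section 5.3.1 specifies a three-level growth model for parent-reported outcomes, with MBC implementation outcomes among the covariates. The Outcome Rating Scale (ORS) and Session Rating Scale (SRS) get a mixed model with fixed effects for time and treatment condition, and session is left out of the mean model in the primary analyses. Section 5.3.4 adds demographic characteristics if they are significantly related to outcome. Time in services is named in none of these places.

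**The concern.** A pre-post contrast is normally read as before versus after the thing being studied. Clinicians have a measurement from before the supports began. Under the synopsis and section 4.1.1, students and parents do not, and some students may already be receiving MBC at the first call.

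Children also enter at different points in treatment. If improvement is faster early on, the change from baseline to month 9 depends on the mix of entry times in the sample as well as on what happened after baseline. Ordinary improvement under treatment and regression to the mean lie inside that change, while any response before the first call lies outside it.

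Two things are at stake. The first is the change estimate, which section 5.3.1 says will be reported with confidence intervals to inform the power analysis of a larger trial. The second is Hypothesis 3, which relates MBC fidelity and use to progress over time. If time in services differed systematically with a clinician's MBC use, the association could partly reflect that difference.

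**Working it through.** The plan gives no effect size, standard deviation or improvement curve for student outcomes, so there is no stated figure to reproduce. The spread of treatment time follows from the documents. The consequence for the change estimate needs an assumed curve and is shown as a range.

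**Step 1: treatment time at each visit.** Inputs are visits at 0, 3, 6 and 9 months, and time already in services at recruitment, s, from 0 to 3 months (section 4.3.2). Taking the baseline call at recruitment, months in services at visit t is t + s.

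- s = 0: 0, 3, 6, 9
- s = 1.5: 1.5, 4.5, 7.5, 10.5
- s = 3: 3, 6, 9, 12

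One visit label therefore spans up to 3 months of treatment, and more if the baseline call comes well after recruitment.

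**Step 2: share of the nine-month change that is seen (assumed curve).** Let improvement by month t be 1 − 2^(−t/h), with half-life h. The change from baseline to month 9 for a student with lag s is 2^(−s/h) × (1 − 2^(−9/h)). Relative to a student measured at entry, the share is 2^(−s/h). Its average over s uniform on 0 to 3 months is [h / (3 ln 2)] × (1 − 2^(−3/h)).

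| Half-life h (months, assumed) | Share at s = 1 | Share at s = 3 | Average, s uniform 0–3 |
|---|---|---|---|
| 2 | 71% | 35% | 62% |
| 3 | 79% | 50% | 72% |
| 6 | 89% | 71% | 85% |
| 12 | 94% | 84% | 92% |

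**Step 3: which adjustment captures this.** Take h = 3. For a student at entry, improvement at the four visits is 0, 0.500, 0.750 and 0.875. With visit deviations −4.5, −1.5, 1.5 and 4.5 (sum of squares 45), the least-squares slope is (−0.750 + 1.125 + 3.9375)/45 = 4.3125/45 = 0.096 per month. At s = 3 it is half of that, 0.048.

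- *Moving the time axis.* Replacing t by t + s adds a constant to all of one student's times, so the deviations, and with them the within-student slope, do not change. In a simulation of a linear growth model with student intercepts (150 students, four visits, s uniform on 0 to 3, h = 3, 60 runs), the mean slope was 0.0695 with visit month and 0.0696 with months since service start.
- *Adding the lag and its interaction with time.* The slope falls by about (0.048 − 0.096)/3 = −0.016 per month of lag. A lag-by-time term estimates exactly this. In a simulation it recovered a slope of 0.095 at entry and an interaction of −0.016.

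**The case against.** The strongest reply is that this is a disclosed feature of a modest pilot. The secondary objective and Hypothesis 3 are worded as associations, and section 3.1 calls the study underpowered. The eligibility rule already limits the sample to recent entrants. Long lags may also be uncommon: section 6.12 ends data collection on June 30, 2023, so a 9-month call for the 2022 cohort needs a baseline by about September 30, 2022, and a 3-month lag would reach back into the summer. This has weight and keeps the point modest. No school calendar is given, however, so the actual spread of lags is unknown. Nor does the plan keep to association throughout: the synopsis speaks of exploring the effect of MBC, and section 2.2 of its effectiveness and impact.

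Several stronger readings are tempting and not supported:

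- *That the three-level model uses study visit as time, or rules out adjustment.* Section 5.3.1 does not define the time metric for that model, and its covariate list is open. Time in services is unnamed, not excluded.
- *That about half the change is lost.* That figure is one assumed half-life at the longest lag.
- *That every student has begun MBC before baseline.* The recruitment wording makes it likely for many, but it is not stated.
- *That Hypothesis 3 is confounded.* Nothing in the documents shows that time in services differs with MBC use.
- *That the direction of bias is known.* Treatment improvement inside the change and response missed before baseline pull in opposite directions, and the documents do not say which is larger.

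**Conclusion.** The point holds as a matter of labelling and model content. Under the synopsis and section 4.1.1 the student comparison has no measurement from before clinician training, although the Table 1 footnote leaves the exact order open. Students first measured 0 to 3 months into services share one baseline label, and a date that would separate them is requested but named in no student model.

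The size is uncertain. For half-lives of 2 to 12 months, the share of change seen at a 3-month lag is 35% to 84%, and the average under uniform entry is 62% to 92%. Both ranges assume decelerating improvement, the second also assumes uniform entry, and neither assumption comes from the documents. If improvement were linear over the period, the lag would not alter the change. Confounding of Hypothesis 3 is a possibility to guard against, not a finding. The comparison can describe change during MBC-supported treatment; it cannot by itself estimate the effect of MBC.

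**What to change.** 1. In section 5.3.1, define the time metric. Add months in services at baseline (baseline date minus service-entry date) and its interaction with time to the student outcome models. Moving a linear time axis to months since service start is not a substitute; it would help only if time were modelled nonlinearly.
2. In the synopsis and section 4.1.1, replace the pre-post label for student and parent outcomes with change from a post-training, early-treatment baseline during MBC-supported treatment. State that this does not by itself estimate the effect of MBC.
3. Reconcile the Table 1 footnote with the synopsis and section 4.1.1 on whether the parent baseline falls after or near training.
4. Report the distribution of months in services at baseline, overall and by clinician, so that a reader can judge how much the adjustment matters.

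The cost is two fixed effects per linear growth model, some missing start dates, and wording. No new data are needed for the parent-reported outcomes. For the ORS and SRS the adjustment works only where a child's record in the online feedback system is linked to the service-entry date. Section 5.1.1 describes both requesting the linking code and using only aggregate data for clinician-level fidelity, so the plan should say which records will be linked. None of this creates a pre-training measurement.

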4.2 Outcome Variables

4.2.1 Primary Outcome Variables

The primary objective of this study is to examine implementation outcomes. Implementation outcomes are selected from a published taxonomy of outcomes include acceptability, appropriateness, feasibility and fidelity. **Acceptability, appropriateness, and feasibility** will be measured by clinician self-report on the Acceptability of Intervention Measure (AIM), Intervention Appropriateness Measure (IAM), and Feasibility of Intervention Measure (FIM) via web-based, clinician-report survey. These 4-item measures were developed based on input from 36 implementation scientists and 27 mental health professionals; structural validity, test-retest reliability, and sensitivity to change have been established. **MBC use (fidelity)** will be evaluated by chart review for evidence of two progress monitoring measures, the Session Rating Scale 3.0 (SRS) and Outcomes Rating Scale 3.0 (ORS). The ORS should be completed before each session to assess prior-week functioning, and the SRS will be completed at the end of the session to assess student/parent perceptions of alliance with the clinician. These will be stored in the Better Outcomes Now (BON) secure online system.

4.2.2 Secondary and Exploratory Outcome Variables

The secondary objective of this study is to examine effectiveness outcomes. **Effectiveness outcomes** of MBC will be measured using actual scores on the SRS and ORS, as documented in the student's service record. The SRS and ORS are part of the Partners for Change Outcome Management System (PCOMS), a system used to enhance patient involvement in mental health services and improve therapeutic alliance and treatment progress. **Student engagement** will be measured by the SRS. **Parent engagement** will be measured by the Therapeutic Alliance Scales for Caregivers and Parents. **Symptoms and functioning** will be measured using the ORS. Emotional and behavioral symptoms will also be measured by the Pediatric Symptom Checklist, 35-item version (PSC-35) which has well-established reliability and validity to assess and monitor progress of internalizing and externalizing symptoms for children ages 4-18. The Therapeutic Alliance Scales for Caregivers and Parents and the PSC-35 will be collected directly from parents/guardians over the phone at baseline and follow-up intervals.

4.3 Study Population

This study plans to enroll 50 SMH clinicians and 150 parents/guardians of children or adolescents receiving SMH treatment from one of the 50 participating clinicians. We anticipate SMH clinicians to be primarily licensed, Masters-level (~95%), in fields of social work (~70%) and counseling (~30%), female (~80%), Caucasian (~70%), median age of 30 years old and 1 to 20 years practicing in SMH. Parents will be enrolled if their child or adolescent is enrolled in mental health services in a participating district and served by a participating SMH clinician. We anticipate parents to be primarily female (~70%) and their children to be representative of students served by SMH clinicians in the districts serving as study sites.

4.3.1 Number of Participants

We plan to work with 50 SMH clinicians and up to 150 parents of children or adolescents with mental illness receiving MBC in SMH services. All SMH clinicians at each district will be invited to participate, and we anticipate approximately 10-40 clinicians from each district depending on their size. All 150 parents of children and adolescents with mental illness receiving MBC in SMH services will be invited to participate. The rationale for this sample size is based on having a large enough sample of clinicians trained that a range of implementation outcomes can be observed and described as pilot data for a larger-scale, fully-powered study. The rationale for the 150 students is based on our prior research in quality improvement and implementation research in schools, where it is more feasible to introduce a new practice to clinicians by telling them they can select a subset of their caseload for MBC implementation. We will outreach to students the clinician reports they are using MBC with. Selection of a subset of cases will involve a random selection of recently consented cases.

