Approximately 150 parents of students working with the participating clinicians will be recruited and enrolled using active consent. Parents will be asked to consent to 1) permission to review student records for goals and progress; and 2) 25-minute study phone calls at baseline, 3-months, 6-months and 9-months to provide parent-reported information on engagement and child outcomes throughout treatment. These data will be used to assess family engagement and child outcomes associated with measurement-based care delivered by the clinicians.

This study will be conducted in established, commonly accepted educational settings where mental health services are routinely provided. The interactions between children, families, their SMH clinicians on school campuses are part of their regular service delivery. The MBC training clinicians provide will be integrated into services as usual. The MBC measures and practices are considered best practices, and evidence-based practices, for children's mental health services. However, clinicians in usual care settings including schools under-implement MBC. They do not pose any risk when integrated into usual care. There are no group assignments. Clinician and parent reported study

measures are retrospective throughout the school year that SMH services are being provided.

Study Date Range and Duration

This study is expected to last approximately two calendar years, with each cohort of clinicians and parents recruited within the 2021-2022 or 2022-23 school year as the participating sites are school districts. Parents will be recruited in fall of 2021, and then again in the fall of 2022, based on clinicians who are signed up to receive the district-required MBC training each fall. Data collection will occur at baseline, 3 months, 6 months and 9 months.

Number of Study Sites (2)

[REDACTED] Public Schools, [ADDRESS REDACTED]

[REDACTED] Public Schools, [ADDRESS REDACTED]

*Other school district sites may be identified depending on their interest in participation.

Primary Outcome Variables

The primary objective of this study is to examine implementation outcomes.

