Implementation outcomes are selected from a published taxonomy of outcomes include acceptability, appropriateness, feasibility and fidelity. **Acceptability, appropriateness, and feasibility** will be measured by clinician self-report on the Acceptability of Intervention Measure (AIM), Intervention Appropriateness Measure (IAM), and Feasibility of Intervention Measure (FIM) via web-based, clinician-report survey. These 4-item measures were developed based on input from 36 implementation scientists and 27 mental health professionals; structural validity, test-retest reliability, and sensitivity to change have been established. **MBC use (fidelity)** will be evaluated by chart review in BON for evidence of two progress monitoring measures, the Session Rating Scale 3.0 (SRS) and Outcomes Rating Scale 3.0 (ORS). The MBC training provided as part of this study will include how to use MBC and document it in BON. The ORS will be completed before each session to assess prior-week functioning, and the SRS will be completed at the end of the session to assess student/parent perceptions of alliance with the clinician.

Secondary and Exploratory Outcome Variables

The secondary objective of this study is to examine effectiveness outcomes.

Effectiveness outcomes of MBC will be measured using actual scores on the SRS and ORS, as documented in the student's service record. The SRS and ORS are part of the Partners for Change Outcome Management System (PCOMS), a system used to enhance patient involvement in mental health services and improve therapeutic alliance and treatment progress. **Student engagement** will be measured by the SRS. **Parent engagement** will be measured by the Therapeutic Alliance Scales for Caregivers and Parents. **Symptoms and functioning** will be measured using the ORS. Emotional and behavioral symptoms will also be measured by the Pediatric Symptom Checklist, 35-item version (PSC-35) which has well-established reliability and validity to assess and monitor progress of internalizing and externalizing symptoms for children ages 4-18. The Therapeutic Alliance Scales for Caregivers and Parents and the PSC-35 will be collected directly from parents/guardians over the phone at baseline and follow-up intervals.

Study Population

This study plans to enroll up to 150 parents/legal guardians of children or adolescents receiving SMH treatment from one of the 50 participating clinicians. We anticipate SMH

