5.2 Study Schedule

Clinician involvement will require approximately 9 hours of project activities during the 2021-22 or 2022-23 school year. All activities are part of their routine services and district-approved professional development schedule. Clinician involvement includes 6 hours of training and ongoing consultation plus 2 hours and 30 minutes of online surveys.

Project activities listed on Clinician Information Sheet will include:

- **A 3-hour interactive training** on measurement-based care in schools. This training will include how to collect, score, and use student- and parent-reported progress measures with students and families to improve engagement, personalize services and inform intervention planning and adjustments throughout the school year.
- **Six, 60-minute, monthly post-training consultation calls** for six months following the training. These calls will be with other participating clinicians and the PI to facilitate peer learning and support for implementing measurement-based care in

schools. Strategies and adaptations to match the school setting and student and family strengths and needs will be discussed.

- **Four, 30-minute online feedback surveys** from clinicians to understand measurement-based care acceptability, appropriateness, and feasibility in schools, plus clinician use of measures and related experiences with implementation. These will occur before the first training and 3 months, 6 months, and 9 months after the training throughout the school year. You will receive a \$25 Amazon gift card for each survey you complete.
- **Collecting student progress data.** You will be asked to collect brief measures of student progress periodically throughout treatment, review it with the student and family and document this in an online system that we will grant you access to called Better Outcomes Now (BON). Collecting and discussing these measures will take 5-10 minutes of session time, 2-4 times per month and will be part of the regular services you already provide. We ask that you do this with at least five (5) of your students.

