- **Parent recruitment.** We will ask you to refer at least five (5) parents to the research study component of this project. We will ask you to present the opportunity to participate in the study to the parents of students you work with. Parent participation is optional and will involve completing four brief phone check ins with one of our study team members during the school year. Parents will receive a \$25 Amazon gift card for each phone check in they complete. If the parent agrees to participate, the study team will also review their BON account for documentation of measures being collected and discussed. We will do this by asking you to provide our study team with their anonymous BON code so we know who the student is in BON. (As administrators, we can access all BON data, but it is deidentified). Records review in BON will occur confidentially by the study team and only if parent permission is provided.

Parent/guardian participation will require approximately 1 hour, 40 minutes of study participation during the 2021-22 or 2022-23 school year. This includes phone consent and four phone interviews of approximately 20-25 minutes each at baseline, 3 months, 6 months and 9 months.

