5.3.2 Sample Size Considerations

We plan to enroll 50 SMH clinicians and up to 150 parents of children or adolescents with mental illness. The rationale for this sample size is based on having a large enough sample of clinicians trained that a range of implementation outcomes can be observed and described as pilot data for a larger-scale, fully-powered study. The rationale for the 150 students is based on our prior research in quality improvement and implementation research in schools, where it is more feasible to introduce a new practice to clinicians by telling them they can select a subset of their caseload for MBC implementation. We will outreach to students the clinician reports they are using MBC with. Selection of a subset of cases will involve a random selection of recently consented cases.

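### The figure of 150 parents invited does not match the plan's own referral requests, and the random draw, as most directly read, comes too late to reduce referral selection

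*Combined protocol and SAP*

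**What the plan says.** The number of parents appears in several forms.

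- Synopsis, Study Design: "Approximately 150 parents of students working with the participating clinicians will be recruited and enrolled using active consent".
- Synopsis, Study Population: "This study plans to enroll up to 150 parents/legal guardians".
- Section 4.3: "This study plans to enroll 50 SMH clinicians and 150 parents/guardians".
- Section 4.3.1: "We plan to work with 50 SMH clinicians and up to 150 parents", and two sentences later "All 150 parents of children and adolescents with mental illness receiving MBC in SMH services will be invited to participate".

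Section 5.2 sets out what each clinician is asked to do. On collecting progress measures it says "We ask that you do this with at least five (5) of your students", and on parent recruitment "We will ask you to refer at least five (5) parents to the research study component of this project". Both are minimums with no stated maximum.

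Sections 4.3.1 and 5.3.2 let clinicians pick part of their caseload for MBC, and direct outreach to the students with whom the clinician reports using it. Both sections end with the same sentence: "Selection of a subset of cases will involve a random selection of recently consented cases".

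The parent recruitment steps in section 5.2.2 are different. The clinician or designated site clinical staff ask the parent about contact, the study team then telephones, and consent is taken. No random draw appears in those steps. No section gives an expected consent rate, a maximum per clinician, or a rule for what happens when 150 is reached.

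**The concern.** Three things look wrong. First, the sentence in section 4.3.1 makes 150 the number invited, while other sentences use 150 as a cap or target for enrolment. Both hold only if nobody declines.

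Second, a draw among consented cases works on a group already shaped by the clinician's choice of MBC students, by whom the clinician or site staff approached, and by who agreed. It can thin that group but cannot make it more like the caseload. Section 4.3 nevertheless expects the children to be representative of students served. Parent engagement is measured by a therapeutic alliance scale, and the rated clinician may control the first approach. It is plausible, though the documents do not show it, that families with a weak alliance are referred less often.

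Third, nothing spreads the places across clinicians. Hypothesis 3 and the three-level model in section 5.3.1 relate MBC use to parent-reported outcomes within clinician clusters. If clinicians who refer early take the places, others contribute no family, and the range of MBC use in that analysis may narrow.

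**Working it through.** **Inputs from the documents.** Clinicians: 50 (sections 4.3 and 4.3.1). MBC students and parent referrals: at least 5 of each per clinician (section 5.2). Parents: 150, as a number invited, a target and a cap (sections 4.3 and 4.3.1). No consent rate or intraclass correlation (ICC) is given, so both are varied below as assumptions.

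**The plan's own figure.** The 150 has a feasibility rationale and no power or precision formula, so there is no calculation to reproduce. The plan's requests give 50 × 5 = 250. Dividing gives 150 / 50 = 3 families per clinician, a number stated nowhere.

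**Yield needed to enrol 150.**

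- If 150 are invited: 150 / 150 = 100%.
- If 250 are referred: 150 / 250 = 60%.

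| Assumed yield | Enrolled from 150 invited | Consenting from 250 referred |
|---|---|---|
| 50% | 75 | 125 |
| 60% | 90 | 150 |
| 80% | 120 | 200 |
| 100% | 150 | 250 |

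With 250 referred, the cap binds only above 60%.

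**Clinicians needed to fill the cap at five referrals each.** This is 150 / (5 × yield): 30 at 100%, 38 at 80% (37.5 rounded up) and 50 at 60%. In the first case 50 − 30 = 20 clinicians (40%) have no family.

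**Cost in precision of that extreme case.** For a clinician-level predictor with k clinicians and m families each, at one time point and with the same spread of the predictor, the variance is proportional to [ICC + (1 − ICC)/m] / k. The comparison is k = 30, m = 5 against k = 50, m = 3, with 150 families in both.

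| Assumed ICC | 30 × 5 | 50 × 3 | Variance ratio | Standard error ratio |
|---|---|---|---|---|
| 0.05 | 0.240/30 = 0.00800 | 0.3667/50 = 0.00733 | 1.09 | 1.04 |
| 0.10 | 0.280/30 = 0.00933 | 0.400/50 = 0.00800 | 1.17 | 1.08 |
| 0.20 | 0.360/30 = 0.01200 | 0.4667/50 = 0.00933 | 1.29 | 1.13 |

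**Order of the selection steps, on the most direct reading.** (1) The clinician chooses students for MBC. (2) The clinician or site staff approach the parent. (3) The parent consents by telephone. (4) A random subset of consented cases is drawn. Step 4 cannot change who passed steps 1 to 3.

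**The case against.** The strongest reply is that the enrolment figures are compatible. Most statements of 150 are ceilings, and 250 referrals with up to 150 enrolled fit at a 60% yield. The 250 is also a count of requests, and clinician uptake of MBC is itself the study question, so fewer may arrive. This stands. The fault is confined to the sentence on invitations, the unstated yield and the missing rule at the cap.

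A reader might infer that a handful of clinicians could fill the study. The documents do not support that at the stated five each: it takes 30 of 50 clinicians with full consent, and more at any lower yield. Ten clinicians would need 15 enrolled families each. That is possible only because at least five has no ceiling. A draw from a complete pool of 250 consenting families would also spread places, with an average of 5 × 150/250 = 3 per clinician. The text does not say that the pool is complete or that the draw is by clinician.

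A reader might also infer that the draw was meant to guard against clinician choice and fails. No section claims that purpose, and the wording does not say what was consented to. It could mean consent to services, since section 4.3.2 requires service entry within three months of recruitment. It could instead mean the subset of consented students used to test the fidelity rubric in section 5.3.1. The first reading sits badly with letting clinicians choose their MBC cases, and sections 5.1.1 and 5.3.1 use consented for study participants. The second leaves parent sampling with no random step. The text needs clarifying on every reading.

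Finally, letting clinicians choose cases is a declared feasibility decision in a pilot that calls itself underpowered (section 3.1). That limits the weight of the point but does not remove it.

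**Conclusion.** The point holds in a limited form and should be corrected. Inviting 150 cannot yield 150 enrolled without 100% consent, while the plan's own requests imply at least 250 families and a 60% yield. As most directly read, the random draw cannot reduce referral selection. It is also missing from the recruitment steps, and no limit per clinician is set.

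Concentration of places arises only if the cap binds and referral is uneven. The loss of 9% to 29% in variance, or about 4% to 13% in standard error, belongs to an extreme case. It rests on assumed ICCs, equal cluster sizes and a single time point, whereas the plan fits a growth model. Any selection bias is additional and cannot be sized from the documents.

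It would be wrong to infer that the main result is at risk. The primary comparison is clinicians' ratings before and after support, and parent sampling does not touch it. The consequence is for the secondary parent outcomes and Hypothesis 3, and for the variance and clustering estimates that section 5.3.1 intends to carry into planning a larger trial.

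**What to change.** 1. In section 4.3.1, replace the sentence on inviting 150 with a statement that at least 250 MBC students are eligible for approach and up to 150 parents will be enrolled, which assumes a 60% yield. Use the same wording in the Synopsis and in sections 4.3 and 5.3.2.
2. Allocate places by clinician: up to three families each first, with unused places released to other clinicians after a stated date in each recruitment year.
3. Remove the draw among consented cases from sections 4.3.1 and 5.3.2. Where a clinician has more MBC students than are to be referred, choose at random within that clinician before anyone is approached, and add this step to section 5.2.2. With exactly five students, a quota of three and 60% consent, 5 × 0.6 = 3, so on average all five are approached and the order matters little. The random step helps mainly where clinicians have more than five.
4. Reconcile that step with the permission and confidentiality wording for the online feedback system in sections 5.1.1 and 5.2, and with Table 1, which places the parent baseline near the initial clinician training. Waiting for a list of MBC students could delay that baseline.
5. Report clinician selection of students for MBC as a remaining limitation, since random choice among students already chosen does not remove it.

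The cost is protocol wording, a simple allocation list and less clinician discretion over whom to refer. The sample size does not change.
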